Study Protocol

Official Title: Remission through Early Monitored Insulin Therapy - Duration Month (REMIT-DM)

ClinicalTrials.gov ID (NCT number): NCT03670641

Protocol Date: 06 July 2021

Scientific Background

REMIT-DM is a feasibility study that aims to show that previously published diabetes remission through early use and titration of short-term insulin therapy is possible and safe in the ambulatory diverse American population of patients with T2D, with continuous glucose level and trend information provided by CGM. We developed the algorithm based on published diabetes remission studies and include within the algorithm the CGM trend arrows to further refine insulin doses for both safety and efficacy purposes. Data captured by the CGM transmits automatically to the cloud and is accessible at any time of day by the multidisciplinary diabetes team, which includes the certified diabetes educator (CDE) and Endocrinologist. The CGM-guided insulin titration algorithm is designed to achieve euglycemia (defined as fasting CBG < 100 mg/dL, and 2 hour post-prandial CBG < 120 mg/dL) within 2 weeks of initiating insulin therapy, then to help maintain euglycemia for 2 weeks before discontinuing insulin entirely. Ten subjects will undergo a maximum of 4 weeks of insulin therapy and will be assessed for remission afterwards to confirm enough recovery of beta cell function. (Complete remission is defined as fasting glycemia <100 mg/dL without use of pharmacological therapy.) Afterwards, we will implement American Diabetes Association (ADA) guidelines for standard glycemic management, as necessary. We will use the data collected during this feasibility study to sharpen the CGM-guided insulin titration algorithm for creation of a T2DM remission mobile application that could then be tested and studied in a larger sample size. The feasibility study will also take into account clinically meaningful data points e.g. the number of phone calls between the patient and the diabetes team, the patient experience, and patient satisfaction.

Study Objectives

Study Design & Methods

Participants will be assessed by the endocrinologist and diabetes educator to be able to perform skills necessary for CGM use and insulin delivery. If the CDE determines that the patient is unable or unwilling to perform the necessary care tasks, this will be communicated to the endocrinologist for potential exclusion from the study.

The Research Activities:

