-Study Visit 1: The PAID-5 survey will be administered to assess diabetes distress by the RN CDE prior to the diabetes education session. Subject will undergo standard of care diabetes self-management education by the study team members, including the initiation of the CGM. OGTT lab blood draw will be done.

-Study Visit 2: Subject will undergo standard of care education for insulin start. Research activity: study team will provide the insulins and instruct the subject in the insulin titration protocol and how CGM readings will be used to manage insulin doses. Subject will adjust their meal-time insulin doses by the before meal blood sugar and the CGM predictive arrows and their daily basal insulin based on how close fasting glucose was to glucose target. Study team will confirm that subject understands how the study works using the teach-back method. Ample time for question and answer will be allotted.

-Study Visit 3: The PAID-5 will be administered at this visit as well as the satisfaction survey. These will both be administered by the RN CDE prior to the education session. If remission is achieved, patient will turn in their CGM and go off their insulin. A repeat OGTT lab blood draw will be done at this time as well. If remission is not achieved, the standard ADA algorithm would apply and patient would be placed back on their medication(s). However, there may be some patients that would prefer to stay on insulin or for which remaining on insulin therapy is

appropriate. The patient will be started on appropriate therapy as guided by clinical decision making.

-Study Visits 4-6: post 4 weeks-1 year patient will have standard of care endocrinology visits driven by clinical decision making.

-Study Visit 7: At 12 months, the PAID-5 and satisfaction survey will again be administered by the RN CDE.

Algorithm Development/Data Analysis Period:

-Post 12 month intervention period: Algorithm and Protocol development

All program data, e.g. number of calls, length of calls, information reviewed/requested on call, documentation of extraneous calls, e.g. after hours/outside of schedule. Clinical outcomes, e.g. rates of hypoglycemia, laboratory results will be analyzed and reviewed. Based on the findings a full protocol that includes the finalized insulin titration algorithm and program processes will be prepared.

Eligibility Criteria

Inclusion criteria:

- Age ≥ 18
- A1C criteria - >7.0
- Diagnosed with T2D within 4 years
- Lifestyle controlled

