- Subject may be on up to 2 medications for diabetes.
- Smart phone or home computer compatible with DEXCOM CLARITY software
- English speaking
- Assessed by endocrinologist and diabetes educator to be able to perform skills necessary for CGM use and insulin delivery

Exclusion criteria:

- Autoimmune Type 1 DM, defined as positive GAD65 or islet cell antibodies
- Pregnant
- Chronic Kidney Disease (CKD) Stage IV or greater
- Mental and/or cognitive disorder (based on documented disorder and/or assessment of physician or educator)
- No access to computer for downloading CGM
- BMI <18.0

Statistical Considerations

This is a feasibility study that does not require power calculation.

Baseline characteristics will be described using measures of central tendencies (means, median, standard deviations). To examine time to glucose target range, hypo/and hyperglycemia, logistic regression will be used. Covariates in the models will include demographic factors, glucose dosing information, insulin protocol used.

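### Logistic regression, with no outcome coding, unit, person-time or clustering stated, is the only model for hypo- and hyperglycemia and does not yield the hypoglycemia rates promised elsewhere

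*Combined protocol and SAP*

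**What the plan says.** Statistical Considerations gives one sentence on method, "To examine time to glucose target range, hypo/and hyperglycemia, logistic regression will be used", and one on adjustment, "Covariates in the models will include demographic factors, glucose dosing information, insulin protocol used". Neither defines hypo- or hyperglycemia. Neither says whether the unit is the participant, the day or the reading, what period is analysed, or how repeated readings and unequal follow-up are handled. The section also states "This is a feasibility study that does not require power calculation".

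Algorithm Development/Data Analysis Period describes a different scale: "Clinical outcomes, e.g. rates of hypoglycemia, laboratory results will be analyzed and reviewed". It names no method for those rates.

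Scientific Background sets the size and duration, "Ten subjects will undergo a maximum of 4 weeks of insulin therapy", and gives the glucose target that the algorithm is meant to reach, "defined as fasting CBG < 100 mg/dL, and 2 hour post-prandial CBG < 120 mg/dL) within 2 weeks of initiating insulin therapy". Those are the only glucose limits for treatment in the plan, and neither is labelled a threshold for hyperglycemia. Entry requires "A1C criteria - >7.0". CGM starts at Study Visit 1, insulin at Study Visit 2, and participants in remission hand back the CGM at Study Visit 3.

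**The concern.** The study is meant to show that the approach is feasible and safe, and to supply data for refining the titration algorithm. Both uses need the frequency, duration and timing of lows and highs. Logistic regression models a binary (or categorical) outcome. Without a stated unit and denominator it says nothing about events per unit of time, so the named model and the promised rates are not connected.

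The text leaves two broad codings open, and each has a problem. Ever/never per participant discards frequency and person-time, and it may leave almost no variation among ten people. Per-day or per-reading coding keeps frequency, but it treats correlated observations as independent unless clustering is specified. At stake is the main safety description of the algorithm: a regression table could be reported that does not show how often lows occurred or whether highs fell during titration.

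**Working it through.** The plan gives no event rate, effect size, power or alpha, so it has no figure to reproduce. The documents supply n = 10, a maximum of 4 weeks on insulin, entry A1C above 7.0, and the target limits. Every event rate and daily probability below is an assumption.

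**1. Ever/never coding, hypoglycemia.** With Poisson events at rate r per week, the same for everyone, P(any in 4 weeks) = 1 − exp(−4r). P(all ten have one) is the tenth power of that.

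| r per week | P(any low) | P(all ten) |
|---|---|---|
| 0.25 | 63.2% | 1.0% |
| 0.5 | 86.5% | 23.4% |
| 1 | 98.2% | 83.1% |
| 2 | 99.97% | 99.7% |

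Doubling the rate from 1 to 2 moves the outcome by 1.8 points. Doubling from 0.25 to 0.5 moves it by 86.5 − 63.2 = 23.3 points. When all ten are positive, the model has nothing to estimate.

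**2. Between-person variation.** Suppose individual rates follow a gamma distribution with shape 1 and mean m. Then P(any) = 1 − 1/(1 + 4m), which is 1 − 1/5 = 80% at m = 1 and 1 − 1/9 = 89% at m = 2. The all-ten probabilities fall to 11% and 31%. The loss of information is then smaller, but doubling the mean rate still moves the outcome by only 9 points.

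**3. Ever/never coding, hyperglycemia.** Let h be the daily chance of at least one reading above the limit used, with days independent. P(any in d days) = 1 − (1 − h)^d.

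| h per day | P(all ten), 14 days | P(all ten), 28 days |
|---|---|---|
| 5% | 0.1% | 7% |
| 10% | 7% | 58% |
| 20% | 64% | 98% |
| 30% | 93% | >99.9% |

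Measured against the target limits (fasting 100, two-hour 120 mg/dL), people who enter with A1C above 7.0 and have up to two weeks to reach target are likely to have at least one high reading. With a higher threshold or a shorter window, that need not be so.

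**4. Exposure.** The design sets "a maximum of 4 weeks of insulin therapy", which permits unequal durations. At 0.25 per week, P(any) is 1 − exp(−0.5) = 39.3% over 2 weeks and 1 − exp(−1) = 63.2% over 4. The odds ratio is (0.632/0.368)/(0.393/0.607) = 2.65 with no difference in rate. Two weeks is a limiting case, used only to show direction and scale.

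**5. Per-day coding.** Four weeks give up to 28 correlated days per participant. For a quantity that differs between participants, such as a demographic covariate, the variance is inflated by roughly 1 + 27ρ, where ρ is the within-person correlation. It at least doubles once ρ reaches 1/27 ≈ 0.037. Per-reading coding has many more observations per person, so the problem is larger.

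**6. What a rate would show.** If all ten complete 4 weeks (40 person-weeks), 40 events give 1.0 per week (exact Poisson 95% interval 0.71 to 1.36) and 80 give 2.0 (1.59 to 2.49). Overdispersion would widen both. The ever/never summary would be near 10/10 in both cases (exact interval 69.2% to 100%).

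**The case against.** The strongest reply is that the plan never says ever/never per participant. A person-day or events-over-trials binomial model is also logistic regression and keeps frequency, and the dosing covariate, which changes over time, fits a repeated unit at least as well. That stands: a reader might infer that the plan commits to yes/no per participant, but the text does not say so. It does not rescue the plan, because a repeated unit needs clustering by participant and none is specified.

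The two sections can also coexist, with rates reviewed descriptively and a regression added on predictors. That stands too. A reader might conclude that the study cannot show how safe or effective the algorithm was. The documents do not support that: rates and laboratory results are to be reviewed, remission is a separate effectiveness outcome, and the OGTT is repeated.

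Two further inferences need limits. Universal hyperglycemia does not follow from the entry A1C, because no hyperglycemia threshold or window is given. A spread of exposure from about 2 to 4 weeks is a possible reading of the design and not a stated plan.

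Finally, the most striking figures arise only at assumed rates of 1 per week or more with no between-person variation. At 0.25 per week the all-ten probability is 1%, and the yes/no outcome keeps more of the information.

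**Conclusion.** The concern holds for the logistic model. As written, the model does not deliver hypoglycemia rates, and it is deficient under either coding: ever/never loses frequency and person-time, and per-day or per-reading coding lacks clustering. How much ever/never coding loses depends on event rates that the documents do not give. Under a common Poisson rate it is severe at 1 or more per week, and it is smaller at lower rates or where people differ. Little or no variation in hyperglycemia is likely against the plan's own target limits, but it depends on the threshold and window chosen. The finding does not extend to the study as a whole. It should be corrected before analysis.

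**What to change.** Make the primary analysis of these two outcomes descriptive by participant.

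- Before analysis, state the CGM limits for low and high glucose, the definition of an episode, the analysis window and the rule for valid wear.
- Report percent CGM time below and above those limits for each participant and insulin week.
- Report hypoglycemia episodes per participant-week of valid CGM wear on insulin. Use intervals that treat the participant as the unit, and caution that with n = 10 they are approximate.
- Show within-person change across insulin weeks, with CGM data from between Study Visits 1 and 2 as the pre-insulin baseline where available.
- Label any regression exploratory, state its unit, and account for clustering by participant.

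The cost is a revision of Statistical Considerations, slightly more analysis work, and wide intervals that will have to be reported as such. The CGM data are already captured, so no visits, procedures or data collection are added.

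### The covariate list for the logistic models is too long for ten participants, and neither the unit of analysis nor any handling of repeated measures is stated

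*Combined protocol and SAP*

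**What the plan says.** Scientific Background sets the size and length of the study: "Ten subjects will undergo a maximum of 4 weeks of insulin therapy". Statistical Considerations gives the model, "To examine time to glucose target range, hypo/and hyperglycemia, logistic regression will be used", and then the adjustment set, "Covariates in the models will include demographic factors, glucose dosing information, insulin protocol used". It adds that a feasibility study needs no power calculation.

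The plan does not state the unit of analysis, the number of covariates, a method for repeated measures, a penalised or exact method, or an exploratory label for the models.

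The documents describe one titration scheme. Scientific Background introduces it with "The CGM-guided insulin titration algorithm is designed to achieve euglycemia", and at Study Visit 2 the team is to "instruct the subject in the insulin titration protocol". The same visit says how doses are set: "Subject will adjust their meal-time insulin doses by the before meal blood sugar and the CGM predictive arrows". Basal doses follow the gap between fasting glucose and its target.

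On use of the results, Scientific Background says "We will use the data collected during this feasibility study to sharpen the CGM-guided insulin titration algorithm", for a mobile application that "could then be tested and studied in a larger sample size". The Algorithm Development/Data Analysis Period section separately says that hypoglycemia rates and laboratory results will be analysed.

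**The concern.** Ten people cannot support a logistic model with several participant-level covariates. With a binary outcome, the rarer class holds at most five of them. The fit often fails to exist, and where it exists it is overfitted. Using days as rows gives up to 280 records, but age, sex or race still take only ten independent values.

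Two of the three covariate groups have a further problem. If everyone follows the one described algorithm, the insulin-protocol covariate has no variation. If the dosing covariate means insulin dose, dose responds to the participant's own glucose. People who are slower to reach target may then receive more insulin because they are slower.

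This is the method the plan names for time to target, hypo- and hyperglycemia, and the data are meant to refine the algorithm. Followed as written, it may return no estimate, or a chance one presented as an adjusted effect.

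**Working it through.** **Inputs from the documents.** Participants: 10. Days on insulin: at most 28 each, so at most 10 × 28 = 280 participant-days. Covariates: three open-ended groups. Dropping the insulin-protocol group as constant leaves at least two covariates; more than one demographic factor makes three or more. The plan has no figure of its own to reproduce.

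**Assumptions, because the documents give none.** Outcome rate 50% to 80%; covariates unrelated to outcome, either all continuous or mixed with 50/50 binary terms; latent-scale intraclass correlation (ICC) 0.1 to 0.5; 28 rows per person when days are rows.

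**1. One row per participant.** The rarer class has at most 5 people, so events per covariate are at most 5/2 = 2.5, 5/3 = 1.7 and 5/4 = 1.25 for two, three and four covariates.

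At a 50% outcome rate with k continuous covariates, Cover's count gives the exact probability of no finite maximum-likelihood fit: the sum of C(9, i) for i = 0 to k, divided by 2^9 = 512.

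- k = 2: (1 + 9 + 36)/512 = 46/512 = 9%
- k = 3: (46 + 84)/512 = 130/512 = 25%
- k = 4: (130 + 126)/512 = 256/512 = 50%

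Simulation extends this to other rates and to binary terms. It uses a linear-programming check for separation, a constant outcome or rank deficiency. The table shows the share with no finite fit, from all continuous to mixed:

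| Covariates | Rate 50% | Rate 70% | Rate 80% |
|---|---|---|---|
| 2 | 9–24% | 18–41% | 34–62% |
| 3 | 25–36% | 39–51% | 56–71% |
| 4 | 50–62% | 61–75% | 75–86% |

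Binary terms explain part of this: one binary covariate alone fails in 22%, 39% and 59%, and one continuous covariate alone in 2%, 7% and 18%. Three-covariate fits that do exist at a 50% rate have a median apparent c-statistic of 0.76 to 0.79, although the true value is 0.50.

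**2. One row per day, hypo- or hyperglycemia.** Simulation: 10 × 28 rows, normal random intercept, one covariate with no true effect, nominal 5% Wald test. The table shows false positives:

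| Covariate and method | ICC 0.1 | ICC 0.3 | ICC 0.5 |
|---|---|---|---|
| Participant-level, clustering ignored | 28% | 48% | 57% |
| Half its variance between people, clustering ignored | 16% | 30% | 41% |
| Varies independently by day, clustering ignored | 5% | 4% | 5% |
| Participant-level, uncorrected cluster-robust variance | 17% | 16% | 16% |
| Participant-level, Mancl–DeRouen correction, t on 8 df | 5.0% | 4.4% | 4.5% |
| Participant-level, regression of participant means | 4.9% | 4.5% | 4.9% |

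With four participant-level covariates and a daily rate of about 0.30, the uncorrected robust variance gave 27% to 32% at ICC 0.05 to 0.3. The corrected method was checked with one covariate only.

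**3. One row per day up to first target.** This is a discrete-time hazard model, with at most one event per person. At assumed daily hazards of 0.07 to 0.10 over 28 days, or 0.10 over 14, equal across people, there were 0% to 2% non-finite fits with one to three covariates and about 4% to 8% false positives. Neither failure above carries over, but at most ten events inform the coefficients.

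**4. The two unclear terms.** A covariate with the same value for everyone is collinear with the intercept and has no estimable coefficient. Dose set from glucose, used to explain when glucose reaches target, mixes the effect of dose with the need for dose.

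**The case against.** The strongest reply is that no logistic model is ruled out once its rows and method are chosen well, and the plan does not commit to the bad choices. Pairing logistic regression with time to target is natural if day rows stop at first target. A corrected clustered model for hypo- or hyperglycemia holds its error rate, and covariates that vary independently by day are unaffected. A reader might infer that adjusted logistic models are unsuitable whatever the rows; the documents and the calculations do not support that. What remains is that the plan states none of these choices, and that good error control does not give ten people useful precision.

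The plan also names no test, p-value or significance level. The false-positive figures therefore apply only if coefficients are tested at 5%. The non-finite fits do not depend on testing.

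The covariate count is not given either. The smallest plausible reading is two, which is why the range starts there.

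Feasibility status excuses the missing power calculation. It does not excuse a named model that often cannot be fitted, and it favours description, because testing is left to a larger sample.

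**Conclusion.** The concern holds in this limited form. With participants as rows, the stated adjustment has no finite fit in 9% to 62% of data sets with two covariates, 25% to 71% with three and 50% to 86% with four. With days as rows for hypo- or hyperglycemia, participant-level covariates give 28% to 57% false positives if clustering is ignored, and 16% to 17% with an uncorrected robust variance. These ranges rest on the assumed outcome rates, covariate types and ICCs. Only the Cover counts are exact, and they too assume a 50% rate and continuous covariates.

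Several stronger inferences should be resisted:

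- The insulin-protocol covariate only appears constant. The Study Objectives heading has no text in the available copy, so variants cannot be excluded.
- The point about dose depends on what the dosing term means. It concerns time to target and does not apply in the same way to preceding dose and hypoglycemia.
- Nothing ties the final algorithm to these odds ratios. Descriptive results, including the separately named hypoglycemia rates, would survive a failed model.

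This should be fixed, but it does not undermine the study as a whole.

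**What to change.** Replace the covariate sentence in Statistical Considerations with, for example:

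> The primary reporting is descriptive, with the participant as the unit: counts with exact 95% confidence intervals; hypoglycemia and hyperglycemia rates per participant; time to target for each participant, with those not reaching target censored at the end of insulin therapy; and individual glucose and insulin-dose profiles. Any regression is exploratory and will state its rows. Participant-row models will use at most one baseline covariate with an exact or penalised method. Day-row models for hypo- or hyperglycemia will use a within-participant or small-sample-corrected clustered method with few covariates. Day-row models for time to target will stop at first target. Insulin dose will not be an adjustment covariate for time to target.

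Define the dosing-information term. Drop the insulin-protocol term unless variants exist and are defined.

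This needs no new data or visits. The cost is that there will be no multi-covariate adjusted odds ratios, and intervals will be wide: 8 of 10 gives an exact (Clopper–Pearson) 95% interval of 44% to 97%, and 5 of 10 gives 19% to 81%. One-covariate models stay weak too. For 3 of 5 versus 2 of 5, the odds ratio is (3/2)/(2/3) = 2.25, the standard error of its log is √(1/3 + 1/2 + 1/2 + 1/3) = 1.291, and the Wald 95% interval is exp(0.811 ± 1.96 × 1.291) = 0.18 to 28.

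### The outcome models adjust for insulin dose, but each dose is a response to the participant's own glucose, so the dose coefficient is confounded and may take the wrong sign

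*Combined protocol and SAP*

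**What the plan says.** The Statistical Considerations section names one modelling approach: "To examine time to glucose target range, hypo/and hyperglycemia, logistic regression will be used". The next sentence lists the adjustment terms: "Covariates in the models will include demographic factors, glucose dosing information, insulin protocol used". Nothing in the study doses glucose, so I read the dosing term as insulin dosing. The unit of analysis (participant, day, meal or sensor reading) is not stated.

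The Research Activities, Study Visit 2, explains how doses arise. For meals: "Subject will adjust their meal-time insulin doses by the before meal blood sugar and the CGM predictive arrows". The background dose is likewise tied to the participant's own readings, since participants set "their daily basal insulin based on how close fasting glucose was to glucose target". The same visit refers to a single protocol, in that staff will "instruct the subject in the insulin titration protocol".

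On size and purpose, the Scientific Background says "Ten subjects will undergo a maximum of 4 weeks of insulin therapy" and "We will use the data collected during this feasibility study to sharpen the CGM-guided insulin titration algorithm". The Algorithm Development/Data Analysis Period section adds: "Based on the findings a full protocol that includes the finalized insulin titration algorithm and program processes will be prepared".

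**The concern.** The dose given at any moment depends on the glucose level just before it, and that level also predicts whether the next reading is high, low or in range. A model containing dose but not the preceding glucose mixes the effect of insulin with the reason it was given. People, days and meals with higher glucose receive more insulin, and this pushes the dose coefficient towards more insulin going with more highs, slower attainment of target and fewer lows.

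This is confounding by indication. It comes from the dosing rule, so more participants would not remove it.

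The data from this study are meant to refine a titration algorithm for a larger study. A misleading association between dose and hypoglycemia would be an unsafe input if anyone took it at face value.

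The protocol covariate has a different problem. If all ten participants use the one algorithm described, it does not vary and its effect cannot be estimated.

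**Working it through.** The plan gives no power, effect size or variance, so there is no figure of its own to reproduce. Every numerical setting below is an assumption chosen to show direction and range. None is a clinical recommendation.

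**1. Protocol term.** With ten rows, an intercept, a constant protocol column and one other covariate, the design matrix has rank 2 for 3 columns. The protocol coefficient is not estimable.

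**2. Meal dose, by hand.** Let P be pre-meal glucose with SD σ. Let dose D = 6 + b(P − 100) + arrow + departure, where departures from the rule have SD δ. Let post-meal glucose = P + 60 + 20·arrow − kD + noise. The true effect is −k mg/dL per unit. Leaving the arrow out for simplicity, the crude slope of post-meal glucose on dose is

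bσ² / (b²σ² + δ²) − k.

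With δ = 0 this is 1/b − k, which has the wrong (positive) sign whenever kb < 1, that is, whenever the rule under-corrects. Sample size does not enter the formula.

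| b | k | σ | δ | Crude slope, mg/dL per unit | Truth |
|---|---|---|---|---|---|
| 0.03 | 8 | 30 | 0 | 33.3 − 8 = +25.3 | −8 |
| 0.03 | 8 | 30 | 2 | 27/4.81 − 8 = −2.4 | −8 |
| 0.03 | 8 | 40 | 2 | 48/5.44 − 8 = +0.8 | −8 |
| 0.1 | 12 | 30 | 0 | 10 − 12 = −2 | −12 |

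All four slopes are biased upwards. Two of them have the wrong sign.

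**3. Meal dose, logistic models.** These simulations kept the arrow, with mean pre-meal glucose 140 mg/dL and residual SD 25. Insulin truly lowers glucose, so the true odds ratio (OR) per unit is below 1 for highs and above 1 for lows.

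| Setting | OR, >180 mg/dL | OR, <70 mg/dL |
|---|---|---|
| Rule followed, b 0.03–0.06, k 3–8 (kb 0.09–0.48), σ 30 or 40 | 1.9–5.3 | 0.08–0.50 |
| b 0.03, k 8, σ 30, departures SD 2 units | 0.97 | 1.04 |
| b 0.03, k 8, σ 40, departures SD 2 units | 1.09 | 0.90 |
| b 0.1, k 12 (kb 1.2), σ 30, no departures, mean post-meal glucose re-set to 150 | 0.91 | 1.16–1.23 |

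**4. Basal dose.** Ten participants over 28 days, with dose titrated on fasting glucose towards 100 mg/dL. The true effect was −2 mg/dL per unit (median). Between-person SD (10, 30, 50), titration gain (0.03, 0.1, 0.2 units per mg/dL) and variation in insulin sensitivity (log-SD 0.1, 0.5) gave 3 × 3 × 2 = 18 scenarios of 150 runs each. A high was fasting glucose of 130 mg/dL or more.

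| Analysis | Runs with the wrong sign |
|---|---|
| Participant level: mean dose and share of high days | 80–100% |
| Participant level: mean dose and time to target | 85–100% |
| Pooled day-level logistic model for highs | 0–96% |
| Within-participant slope of glucose on dose | 0% in all 18 |

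The participant-level rows are correlations, not logistic fits. Other covariates were left out, and the sign for lows was not examined in this basal model.

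**5. Sample size.** In a separate basal simulation (true effect −1.5 mg/dL per unit), mean dose correlated about +0.82 with the share of high-fasting days in studies of ten, and +0.78 with 2,000 participants.

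**The case against.** The strongest reply is that reversal is not established. A reader might infer that dose coefficients must come out with the wrong sign. The documents do not support that. They give neither the unit of analysis nor how fully the algorithm corrects, nor how closely participants follow it, and the checks show that the answer turns on these. The large odds ratios belong to one assumed corner, where every dose under-corrects and nobody departs from the rule. This objection stands against any claim of certain reversal. It leaves the confounding untouched: a coefficient whose sign depends on unstated features cannot be interpreted.

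A second reply is that dose is only a covariate, and that no sentence says its coefficient will be interpreted or will drive the revised algorithm. A reader might infer that the coefficient feeds straight into the revision. The text does not say so: call data, hypoglycemia rates and laboratory results are reviewed as well. This also stands, so the harm is a risk and not a stated step. Even so, these are the only models specified, and the revision is to rest on the findings. Adjusting for dose also turns the demographic coefficients into comparisons at equal dose, which is not an evident aim.

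Third, the terms are undefined. The dosing term could mean mean dose, dose per event or dose per kg, and listing a protocol term hints that versions might differ. The covariate list is also not said to be complete, so glucose could still be added. All fair, but the written list names no glucose measure, and only one algorithm is described.

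**Conclusion.** The point holds in limited form. Read as written, the models include dose without the glucose that determined it, so the dose coefficient is confounded by insulin need, and a larger sample would not cure this. Sign reversal is possible. Under the settings tried it was usual in participant-level summaries (80–100% of runs) and ranged from never to nearly always in pooled day-level models (0–96%). In meal-level models it was strong when the rule was followed and under-corrected, and slight or absent with 2-unit departures or stronger correction. These sizes rest wholly on assumed inputs and are not estimates for this trial.

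The protocol term carries no information if all ten use the one algorithm described. Dropping it then changes no result.

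The plan should be corrected, because the data are to inform the algorithm. With ten subjects, a feasibility aim and no stated hypothesis test, the correction is not a precondition for running the study.

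**What to change.** In Statistical Considerations:

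- Remove dosing information from the covariate list and report doses descriptively over time.
- Drop the protocol term unless versions of the algorithm differ. If they do, define them.
- State the unit of analysis for each outcome.
- For algorithm revision, tabulate CGM outcome after each meal dose (low, in range, high) within bands of pre-meal glucose by trend arrow. Show the number of participants as well as doses in each cell. Three meals a day for 28 days, an assumption, would give 84 meals per person and 840 in all, so some cells will be thin and will rest on few people. The table shows how the algorithm performed as applied; it does not estimate a dose effect.
- If dose is modelled at all, do it within participant, include the preceding glucose and arrow, handle clustering, and give the dose coefficient no causal reading. Where the rule is followed closely, little can be learned this way: in the meal simulation, pre-meal glucose and arrow explained 96–99% of dose variance.
- Optionally, where both are already captured, compare the algorithm's dose with the dose taken. Departures are what carry separate information on dose.

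The cost is a few sentences and one simple table, and there would be no dose-adjusted coefficients. No dose or clinical rule changes.
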